10.3 Monitoring

The condition of each subject will be monitored from the time of signing the ICF to final discharge from the investigation. Subjects will be observed for any signs or symptoms and asked about their condition by open questioning, such as "How have you been feeling since you were last asked?" at least once each day at each investigation visit. Subjects will also be encouraged to spontaneously report AEs occurring at any other time during the investigation.

All nonserious AEs, whether reported by the subject voluntarily or upon questioning, or noted on physical examination, will be recorded from initiation of investigation treatment until investigation completion. Serious AEs will be recorded from the time the subject signs the ICF until investigation completion. The nature, time of onset, duration, and severity will be documented, together with an Investigator's, or designee's, opinion of the relationship to investigation treatment.

If an AE occurs, appropriate diagnostic and therapeutic measures are to be taken and the investigational treatment must be discontinued if appropriate. Follow-up evaluations of the subject

are to be performed until the subject recovers or until the clinical Investigator considers the situation to be no longer clinically significant.

If clinically significant laboratory abnormalities appear at the final treatment, appropriate additional tests may be performed to clarify the nature of any clinically significant laboratory abnormalities that occur.

10.4 Assessment of Severity

The site Investigator will be asked to provide an assessment of the severity of the AE using the following categories:

Event Severity	Severity Definition
Mild	Usually transient and may require only minimal treatment or therapeutic intervention. The event does not generally interfere with usual activities of daily living. The AE does not influence performance or functioning. Prescription drugs are not ordinarily needed for relief of symptom(s).
Moderate	Usually alleviated with additional specific therapeutic intervention. The event interferes with usual activities of daily living, causing discomfort but poses no significant or permanent risk of harm to the participant. Performance of daily activities is influenced. Treatment of symptom(s) may be needed.
Severe	Interrupts usual activities of daily living, or significantly affects clinical status, or may require intensive therapeutic intervention. Treatment for symptom(s) may be given.

10.5 Relationship to Investigation Treatment

The site Investigator will determine the relationship of the AE to the investigational device according to the following guidelines:

Event Relationship	Relationship Definition
Unrelated	The adverse event is reasonably expected to be related to (or caused by) a concurrent illness, effect of another device/drug or other cause, and is unlikely related to the investigational product.
Possibly Related	The adverse event is reasonably expected to be related to the investigational product, and an alternative etiology is equally or less likely compared to the potential relationship to investigational product.
Probably Related	There is a strong relationship to investigational product, or recurs on re-challenge, and another etiology is unlikely, or there is no other reasonable medical explanation for the event.

10.6 Action Taken for Adverse Events

The site investigator or designee will record the action taken for the AE in the Case Report Form. Actions taken will include:

Action	Action Definition
Treatment Interrupted	The treatment was modified by temporarily terminating the treatment.
Treatment Withdrawn	The treatment was modified through termination of the treatment.
Not Applicable	No action is needed.
Unknown	The action is unknown or to be determined.

10.7 Follow-up of Adverse Events

Every reasonable effort will be made to follow up with subjects who have AEs. Any subject who has an ongoing AE that is related to the investigational medical device during visits will be followed up with, where possible, until resolution. This will be completed at the site investigator's (or designee's) discretion. Any subject who has an ongoing AE that is not related to the investigational medical device at follow-up visits can be closed out as ongoing at the Investigator's discretion.

10.8 Reporting

10.8.1 Device Issue or Deficiency

Any issues regarding the operation of the device or any malfunctions are to be reported to the sponsor. All reported issues will be processed per the Manufacturer's standard operating procedures outside of the study. Information about device issues to be provided to manufacturers will include a description of the event, dates of onset and resolution, action taken, and the outcome.

Copies of all issues documentation submitted to manufacture(s) will be stored as part of the study record. If additional information is needed from sites or investigators, the Sponsor or its delegate may contact the investigator for follow-up information necessary to investigate reported device issue.

It is the responsibility of the site investigator to report any issues associated with a medical device distributed by the Sponsor, regardless of whether they are related to intended use, misuse, or abuse of the product. Reporting must be done as soon as possible (within 48 hours).

10.8.2 Adverse Events

Adverse events are monitored and registered at each visit. In absence of a specific diagnosis, an individual AE form must be filled in for each sign or symptom. Adverse events will be reported to the local IRB as required by their policy and monitored by the Sponsor's delegated monitor.

Persistent AEs will be recorded once until they are resolved or if a new event must be documented due to deterioration. These AEs will be carefully monitored; further details of monitoring of persistent AEs will be provided in the monitoring plan. If an AE is still not resolved at the end of the investigation, this will be documented as ongoing.

For recurrent AEs (i.e., AEs of the same nature, but with a different date of onset), an individual AE form must be completed for each of them.

Adverse events occurring after the termination of the investigation individually and/or of the investigation in total are to be reported to the Sponsor even after the clinical investigation has been finished if, in the judgment of the Investigator, there is an association between the event and the previous use of the Device under investigation.

10.8.3 Anticipated/Unanticipated Adverse Device Effect

All relevant observations, including records concerning adverse device effects (whether anticipated or unanticipated) will be recorded of each subject's study record, per 21 CFR 812.140 or relevant national regulation.

The site investigator will notify the Sponsor or designee and reviewing IRB in writing (e.g., facsimile) immediately, but no later than 72 hours of when an UADE, that is potentially FDA reportable, is first recognized or reported.

The sponsor will immediately conduct an evaluation of any UADE reported. The sponsor will report the results of the evaluation to FDA and to all reviewing IRB and participating investigators within 10 working days after the sponsor first receives notice of the effect. Thereafter the sponsor will continue to submit additional reports to the FDA when requested.

If the sponsor determines that an UADE presents an unreasonable risk to subjects, the sponsor shall terminate all investigations or parts of investigations presenting that risk as soon as possible. Termination shall occur not later than 5 working days after the sponsor makes this determination and not later than 15 working days after the sponsor first received notice of the effect.

11.0 EARLY TERMINATION OR SUSPENSION

11.1 Study Closure, Early Termination or Suspension Criteria

Study closure is defined as closure of a clinical study that occurs when GN Hearing A/S and/or regulatory requirements have been satisfied per the protocol and/or by a decision by GN Hearing A/S or regulatory authority, whichever occurs first. Study Closure is a process initiated by distribution of an initial study closure letter. The study closure process is complete upon distribution of the Final Report or after final payments, whichever occurs last.

The study may be terminated early if the Sponsor determines that unanticipated adverse event(s) presents an unreasonable risk to subjects or for any other reason as Sponsor determines to be appropriate. Termination shall occur no later than five (5) working days after the sponsor makes the determination and no later than fifteen (15) working days after Sponsor first received notice of the effect.

The Sponsor will promptly notify the Investigators of any determination to terminate the study outside of the protocol timeframe. The Sponsor will provide each Investigator with written guidelines/instructions on termination processes and timelines. The Investigator is responsible for reporting the early termination to their local IRB.

Possible reasons for considering study suspension or termination of the study for all centers include but are not limited to AEs and device deficiencies associated with the system or product under investigation which might endanger the safety or welfare of subjects; observed/suspected

performance different from the product's design intent; cancelation of device development; and/or a decision by GN Hearing A/S or regulatory body.

Possible reasons for clinical investigator or center termination or suspension include but are not limited to a failure to obtain initial IRB approval or annual renewal of the study; consistent non-compliance to the protocol; lack of enrollment; noncompliance to regulations and the terms of the Clinical Study Agreement, such as failure to submit data in a timely manner, failure to follow-up on data queries and monitoring findings in a timely manner, etc.; IRB suspension of the center; fraud or fraudulent misconduct, as defined by local law and regulations; and/or Investigator request.

11.2 Withdrawal of IRB Approval

The site investigator is to notify the Sponsor of any withdrawal of IRB approval within 5 working days of such occurrence. If the IRB terminates or suspends its approval of the Study, the site investigator will promptly notify Sponsor and provide a detailed written explanation of the termination or suspension. Upon receipt, the sponsor will provide written guidelines/instructions on subject withdrawal/termination processes and timelines.

12.0 INSTITUTIONAL REVIEW BOARD (IRB) AND REGULATORY REQUIREMENTS

12.1 Regulatory Requirements

To ensure the quality and integrity of research, this study will be conducted according to 21 CFR Part 812 and related regulations, principles of ISO 14155 Good Clinical Practice (GCP), and the Declaration of Helsinki and its amendments.

12.2 IRB Approval Requirements

To approve the research described in the Clinical Investigation Plan (CIP), the IRB shall determine that all the following are satisfied in accordance with 21 CFR 56.111.

- Risks to subjects are reasonable in relation to anticipated benefits
- Selection of subjects is equitable
- Informed consent will be sought and appropriately documented
- Data will be monitored and collected, where appropriate, to ensure the safety of subjects
- Safeguards have been included to protect the rights and welfare of subjects that are likely to be vulnerable to coercion or undue influence

This investigation will be conducted in accordance with the CIP and with the following:

- Consensus ethical principles derived from international guidelines including the Declaration of Helsinki and Council for International Organizations of Medical Sciences International Ethical Guidelines
- Applicable International Organization for Standardization (ISO) Good Clinical Practice (GCP) Guidelines
- Applicable regulations:
 - 21 CFR 50, *Protection of Human Subjects*, provides the requirements and general elements of informed consent;
 - 21 CFR 56, *Institutional Review Boards*, covers the procedures and responsibilities for institutional review boards (IRBs) that approve clinical investigations protocols;
 - 21 CFR 54, *Financial Disclosure by Clinical Investigators*, covers the disclosure of financial compensation to clinical investigators which is part of FDA's assessment of the reliability of the clinical data.
 - 21 CFR 820 Subpart C, *Design Controls of the Quality System Regulation*, provides the requirement for procedures to control the design of the device in order to ensure that the specified design requirements are met.

Where applicable and consistent with local regulations and prior to enrolment of subjects, the CIP, CIP amendments, Informed Consent Form (ICF), Investigator Brochure, and other relevant documents must be submitted to an IRB by the Investigator and reviewed and approved by the IRB before the investigation is initiated. Any additional requirements imposed by the IRB or regulatory authority shall be followed, if appropriate. Enrollment will not start before written confirmation of approval from the relevant central or local IRB.

The site investigator will be responsible for the following:

- Providing written summaries of the status of the investigation to the IRB annually or more frequently in accordance with the requirements, policies, and procedures established by the IRB.
- Notifying the IRB of serious adverse events or other significant safety findings as required by IRB procedures.
- Providing oversight of the conduct of the investigation at the site and adherence to requirements of 21 Code of Federal Regulations (CFR), ISO 14155 guidelines, the IRB, and all other applicable local regulations.

12.3 Subject Compensation

Participants who fail the inclusion criteria will be compensated \$60. All others will be compensated at a rate of \$60 for each of the three lab sessions plus \$70 for the wear trial (a total of \$250). Payment will be given at one time at the end of the study.

12.4 CIP Revision/Amendment Management

Changes to the CIP will be documented in written CIP amendments. Major, substantial or significant, amendments will usually require submission to the relevant IRB for approval. In such cases, the amendment will be implemented only after approval from the IRB has been obtained, except for changes necessary to eliminate an immediate hazard to investigation subjects. Minor,

non-substantial, CIP amendments, including administrative changes, will be filed by the designee at each participating site and will be submitted to the relevant IRB or regulatory authorities where required by pertinent regulations. Any amendment that could have an impact on the participant's agreement to participate in the study requires the participant's informed consent prior to continued participation in the study.

12.5 Informed Consent and Privacy Requirements

12.5.1 Informed Consent

Informed consent is a process that is initiated prior to the individual's agreeing to participate in the study and continues throughout the individual's study participation. Consent forms will be IRB/IEC-approved, and the subject will be asked to read and review the document. The investigator will explain the research study to the subject and answer any questions that may arise. A verbal explanation will be provided in terms suited to the participant's comprehension of the purposes, procedures, and potential risks of the study and of their rights as research subjects. Subjects will have the opportunity to carefully review the written consent form and ask questions prior to signing. The subjects should have the opportunity to discuss the study with their family or surrogates or think about it prior to agreeing to participate. The subject will sign the informed consent document prior to any procedures being done specifically for the study. Subjects must be informed that participation is voluntary and that they may withdraw from the study at any time, without prejudice. A copy of the informed consent document will be given to the subjects for their records. The informed consent process will be conducted and documented in the source document, including the date, and the form provided, before the subject undergoes any study-specific procedures. The rights and welfare of the subjects will be protected by emphasizing to them that the quality of their medical care will not be adversely affected if they decline to participate in this study.

The informed consent forms (ICFs) will describe in detail the study intervention, study procedures, and risks are given to the participant, and written documentation of informed consent is required prior to the study start.

The site investigator or authorized designee must administer the approved ICF to each prospective study patient without coercion or undue improper influence on, or inducement of, the patient to participate. During the consent discussion the site investigator (or designee) must fully inform the patient of all pertinent aspects of the study, using native non-technical language that is understandable to the patient. The subject must be informed about their right to withdraw from the study at any time and for any reason without sanction, penalty, or loss of benefits to which the subject is otherwise entitled and also informed that withdrawal from the study will not jeopardize their future medical care. The subject must also be informed that by participating in the study, they are not waiving their legal rights. The patient must have ample time and opportunity to inquire about details of the study, and to decide whether or not to participate in the clinical study. All

questions about the study should be answered to the satisfaction of the participant. All items discussed in the ICF must be explained.

The ICF should be revised whenever there are changes to procedures outlined in the informed consent or when new information becomes available that may affect the willingness of the subject to participate. For any updated or revised ICFs, the medical file for each subject should document the informed consent process and that written informed consent was obtained for the updated/revised ICF for continued participation in the study.

12.5.2 Privacy Requirements

Subject confidentiality and privacy is strictly held in trust by the participating investigators, their staff, and the sponsor(s). All health data collection is conducted in a manner compliant with 21 CFR Part 11 and applicable data privacy law and regulation in the US. Therefore, the study protocol, documentation, data, and all other information generated will be held in strict confidence. No information concerning the study, or the data will be released to any unauthorized third party without prior written approval of the sponsor. Additionally, all research activities will be conducted in as private a setting as possible.

Data protection and privacy regulations will be strictly observed in capturing, forwarding, processing, and storing subject data. Every effort will be made to protect subject confidentiality. To maintain patient confidentiality, each patient will be assigned a unique subject identifier upon study enrolment. This subject identifier will be used in place of subject name for data analysis and reporting. Medical record number or other local reference identifiers are not collected as part of the database. All parties will ensure protection of subject personal data and will not include subject names on any study forms, reports, publications, or in any other disclosures, except where required by law. In accordance with local regulations in each of the registry countries, subjects will be informed about data handling procedures and asked for their consent. Data protection and privacy regulations will be observed in capturing, forwarding, processing, and storing patient data.

The study monitor, other authorized representatives of the sponsor, representatives of the IRB, regulatory agencies or Sponsor supplying study product may inspect all documents and records required to be maintained by the investigator, including but not limited to, medical records for the subjects in this study. The clinical study site will permit access to such records.

Subjects will be assigned a unique identifier and will not be identified by name in electronic databases, investigation-related forms, investigation reports, or any related publications. Subject and Investigator personal data will be treated in compliance with all applicable laws and regulations. In the event the CIP, investigation report, or investigation data are included in a public registry, all identifiable information from individual subjects or Investigators will be redacted according to applicable laws and regulations.

The subject must be informed that her personal investigation-related data will be used by the Sponsor in accordance with local data protection law. The level of disclosure must also be explained to the participant. The subject must also be informed that her investigation-related data may be examined by Sponsor or Contract Research Organization (CRO) auditors or other

authorized personnel appointed by the Sponsor, by appropriate IRB members, and by inspectors from regulatory authorities.

13.0 DATA AND QUALITY MANAGEMENT

This study will be performed by Northwestern University, Sertoma Speech and Hearing Center, and Vanderbilt University with guidance, input, review, and approval of GN Hearing A/S, including development of materials, recruitment, training and management of the site, electronic data capture and data management.

13.1 Management of Data

High data quality standards will be maintained, and processes and procedures utilized to repeatedly ensure that the data are as clean and accurate as possible when presented for analysis. Data quality will be enhanced through a series of programmed data quality checks that automatically detect out of range or anomalous data.

The following practices are adopted to ensure data integrity and participant safety:

1. Data, including outcomes data, should not be shared with GN Hearing A/S until study completion. There are two components to this study: (1) in-lab session (Visit 1); and wear-time crossover trial (Visits 2 and 3). Outcome data can be shared with GN Hearing A/S at the completion of each component to this study. That is, the results from Visit 1 can be shared with the sponsor as soon as they are available and prior to the completion of the entire study.
2. The site investigators should be blinded from the raw data and the research staff on site should enter the data into an electronic database (REDCap). Weekly reports of completed data for each visit will be generated by research staff at each site and will be sent to [name]. Progress reports, generated by [name], will tabulate the number of subjects who have complete data for Visit 1, Visit 2, and Visit 3, for each site separately and combined. Such progress reports will be provided via email to GN Hearing A/S ([name] and [name]) and shared with the site investigators ([name], [name]) on a weekly basis.
3. [name] will monitor the quality of the data exported from REDCap. PRO-FIT REAG values will be checked to determine that they are reasonable, within 5-7 dB of NAL targets, for the measured pure-tone hearing loss for that participant. The pattern across frequency for the REAG differences between test and retest will also be examined to assess data validity. Such differences should generally be less than 5 dB at a given frequency and also should not decrease with increasing frequency. Concerns about the quality of data being gathered will be shared with each site investigator and GN Hearing A/S as soon as possible.

4. Trained research staff at each site should report any concerns about the quality or validity of the raw data being obtained to the local site investigator immediately and this feedback should be shared among the two site investigators and [name] immediately to determine if protocol amendments are warranted to address these concerns.
5. At study completion at each site, [name] will be primarily responsible for data reduction and analyses with drafts shared with GN Hearing A/S and that site's PI. When both sites have completed data collection, [name] will complete the data reduction and analyses, draft a report, and share this report with both site PIs and GN Hearing A/S.
7. Any adverse events experienced by the participants should be reported by the site investigator to [name] and [name] with serious adverse events reported immediately to GN Hearing A/S and the FDA as well. See Section 10.0 for additional details.

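### Two-site wording left in a three-site protocol makes the Section 13.1 analysis and release rules, and the per-site subject counts, wrong as written

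*Combined protocol and SAP*

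**What the plan says.** Number of sites: Sections 4.1 and 6.3 give three, Section 13.0 names three, and the sequence plan in Section 6.2.5 is written for three.

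Section 13.1, on access and analysis:
- Item 1 opens with a bar: "Data, including outcomes data, should not be shared with GN Hearing A/S until study completion". It then divides the study into the in-lab session (Visit 1) and the wear-time crossover (Visits 2 and 3), and continues: "Outcome data can be shared with GN Hearing A/S at the completion of each component to this study". It explains this by adding that "results from Visit 1 can be shared with the sponsor as soon as they are available and prior to the completion" of the whole study.
- Item 2 sets a safeguard: "The site investigators should be blinded from the raw data".
- Item 4, on data-quality concerns, says that "this feedback should be shared among the two site investigators".
- Item 5 provides, at each site's completion, for "data reduction and analyses with drafts shared with GN Hearing A/S" and with that site's principal investigator. A separate sentence sets the combined analysis: "When both sites have completed data collection", the analyst completes the analyses, drafts a report and is to "share this report with both site PIs and GN Hearing A/S".

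Per-site numbers: Section 5.1 plans 36 subjects at 18 per site and calls 32 the minimum for adequate power. Section 6.2.5 first puts two subjects in each of six sequences at each of three sites, six per sequence overall. A few lines later it has 9 subjects at each site start the crossover with SELF-FIT A and the other 9 with PRO-FIT.

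**The concern.** Item 5 treats completion at one site and completion of data collection overall as separate events, and sends analysis drafts to the sponsor at the first. A site that has finished has its Visit 2 and Visit 3 data, including APHAB, the primary endpoint of the field trial. The other sites may still be running crossovers. That is not what the opening of item 1 allows, and the component-wise release in item 1 does not clearly allow it either.

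The trigger for the combined analysis names a number of sites that the study does not have. An analyst following it literally could begin with one site outstanding. The per-site counts matter in the same practical way: sites assign subjects to sequences from them, and the two sets of counts cannot both be followed.

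At stake are a clear record of who could see which results and when, an analysis set that is complete when the combined analysis starts, and the planned counterbalancing.

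**Working it through.** **1. The plan's own sample-size figure.** Section 5.1 gives a margin of 0.084, crossover root MSE of 0.115, a true difference of 0, a 2.5% test and 16 subjects per sequence group (32 in all).
- SD of differences = 0.115 × √2 = 0.1626 (the plan rounds to 0.163).
- Standard error = 0.1626 / √32 = 0.02875.
- Noncentrality = 0.084 / 0.02875 = 2.92, with 30 degrees of freedom.
- Power from the noncentral t distribution = 80.7%, which agrees with the stated 80%.

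The minimum of 32 is therefore sound on the plan's inputs and can serve as a benchmark below.

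**2. Per-site counts.**

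| Source | Per site | × 2 sites | × 3 sites |
|---|---|---|---|
| 5.1: 18 per site | 18 | 36 | 54 |
| 6.2.5: 9 + 9 at each site | 18 | 36 | 54 |
| 6.2.5: 2 subjects × 6 sequences | 12 | 24 | 36 |

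Only the last row gives the planned total of 36 at three sites. It also matches the stated six subjects per sequence overall (2 × 3 = 6, and 6 × 6 = 36). Eighteen per site would need 18 / 6 = 3 subjects per sequence at each site, but Section 6.2.5 says two. The requirement in Section 5.1 of equal numbers in the three in-lab orders does not settle it, because both counts divide by three (18 / 3 = 6, 12 / 3 = 4).

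**3. Wear-time orders.** If the six sequences are the three in-lab orders crossed with two wear-time orders, 12 per site splits into 6 and 6. Over three sites that is 6 × 3 = 18 per order, above the 16 in Section 5.1. Nine per order per site would give 9 × 3 = 27 per order. The crossing is an assumption here, because the study-flow figure is not in the text available.

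**4. The combined-analysis trigger.** With 12 per site, two completed sites give 24 subjects: 24 / 36 = 67% of the planned total, and 8 short of the minimum of 32.

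**5. The site-level drafts.** If sites finish at different times, drafts could cover 12 / 36 = 33% of subjects after the first site and 24 / 36 = 67% after the second. These are shares of the data that could be seen, not effects on the result.

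**6. Item 1 against item 5.** Item 1 gives a bar, then release by component, then Visit 1 as the worked example. The last two can be read together as an exception to the first. Item 5 fits neither: its trigger is a site, not a component, and nothing in it limits drafts to Visit 1.

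**The case against.** Several points on the other side have force.

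- **Item 1 is not a flat contradiction.** It reads naturally as a general bar followed by a deliberate exception for staged release, and a sponsor may choose that. This stands. What remains is that the first sentence is unqualified and that completion of the component is not defined across sites, so rolling release of Visit 1 results is not excluded.
- **Item 5 speaks of study completion site by site,** so study completion in item 1 might mean the same. Against this, item 1 itself contrasts early Visit 1 release with completion of the entire study.
- **Two investigators might cover three sites.** Item 2 of Section 13.1 has two name placeholders for the site investigators. This stands for the mentions of two investigators and of both principal investigators, which should be checked and not simply changed to three. It does not rescue the reference to both sites.
- **The content of a site-level draft is not stated.** Hence the claim is only that a draft may include APHAB results.

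A reader might also infer an undeclared interim analysis that breaches Section 8.2. The documents do not support that: item 5 describes no test on partial data, decision rule or stopping action.

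Nor do they show that early sponsor knowledge biases the APHAB comparison. APHAB is completed by the subject, the PRO-FIT settings are not retuned during the study (6.2.2), and site investigators are to be kept from the raw data. The numerical margins are fixed in advance (3.1), and success requires all primary endpoints (8.4). The sponsor's powers over termination (11.1), its part in replacing subjects (6.5) and its oversight role (13.0) are general. No passage ties them to outcome results.

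**Conclusion.** The point holds as an error in the current text. The reference to both sites in item 5 cannot be right for three sites. Read literally with 12 subjects per site, it allows a combined analysis on 24 of 36 subjects, against a required 32. The site-level drafts could reach the sponsor while collection continues elsewhere; that depends on sites finishing at different times and on what a draft contains, neither of which is stated. The counts of 18 per site and 9 + 9 per site imply 54 subjects at three sites. A reader might take 54 as an intended enrolment, but the stated total is 36 throughout and the sequence plan in Section 6.2.5 reaches it exactly.

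The last entry in the version table, which records the change from two to three sites, explains the likely origin. The error itself lies between current sections. Item 1 needs clarification only. No type I error inflation, loss of power or demonstrated bias is claimed. Confidence is high on the textual mismatches. The changes should be made because sites and analysts would act on these rules and numbers.

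**What to change.** 1. **Section 13.1 item 5.** Replace the per-site analyses and drafts with one wear-time outcome analysis after the last Visit 3 at all three sites and database lock. Change the trigger to all three sites. Check the mentions of two site investigators (item 4) and both principal investigators (item 5) against the actual investigator list.
2. **Sections 5.1 and 6.2.5.** Restate the plan as 12 subjects per site. Restate the crossover split as 6 and 6 at each site, once it is confirmed that the six sequences are the three in-lab orders by two wear-time orders.
3. **Section 13.1 item 1.** Qualify the opening bar so that staged release of Visit 1 results is an explicit exception. Define completion of that component as the last Visit 1 at all three sites, with no rolling release. Whether to keep staged release at all is the sponsor's choice.

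Completion counts, safety reports and data-quality concerns can continue to flow as now. The cost is a wording amendment and a longer wait by the sponsor for site-level results. Sample size, margins and tests do not change.
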